3.1.1.3. Safety Review Team

A safety review team (SRT) will be established to assess safety of patients across the cohorts.

The SRT will consist of at least 1 investigator, a Gilead safety physician, and the Gilead medical monitor. Others may be invited to participate as members of the SRT if additional expertise is desired. The medical monitor serves as the chair of the SRT. An SRT charter (or similar document) will be agreed on by all SRT members prior to the first SRT meeting. The data reviewed at the SRT meeting to make decisions will be defined in the SRT charter (or similar document). The quality control checks performed on the data reviewed and used for making decisions will be described in the SRT charter (or similar document).

3.1.2. Phase 2 Cohorts

After completion of each safety run-in cohort and identification of the RP2D for that cohort, the corresponding Phase 2 cohort may be enrolled as follows:

- Phase 2 Cohort 1 (1L Unfit AML Mag+Ven+Aza), closed to enrollment globally as of *Protocol Amendment 5*: 40 patients with newly diagnosed, previously untreated AML who are ineligible for intensive chemotherapy will be enrolled to receive magrolimab + venetoclax + azacitidine
- **Phase 2 Cohort 2 (R/R AML Mag+MEC):** 30 patients with R/R AML will be enrolled to receive magrolimab + MEC.
- Phase 2 Cohort 3 (Post-chemo Maint Mag+CC-486), closed to enrollment globally as of *Protocol Amendment 5*: 40 patients with newly diagnosed AML who are in CR or CRi with MRD positivity following intensive chemotherapy may be enrolled to receive magrolimab + CC-486.

Up to 5 to 10 additional patients may be enrolled in each of the Phase 2 cohorts to collect additional safety, efficacy, and/or PK/PD data.

3.1.3. Closure of Cohorts 1 and 3

Cohort 1 closed to enrollment globally as of Protocol Amendment 5 and no new patients enrolled in Cohort 1 thereafter. A total of 18 patients were enrolled into Cohort 1 (7 patients in safety run-in and 11 patients in Phase 2).

Cohort 1 patients enrolled prior to sponsor's notification and implementation of Protocol Amendment 5 will continue on study, receive study treatment (Sections 3.3, 5.1, and 5.2), and undergo all study assessments (Section 6), until end of study or discontinuation criteria are met (Sections 3.4 and 3.5).

Cohort 3 closed to enrollment globally as of Protocol Amendment 5 and no patients were enrolled.

3.2. Study Treatments

Study treatments for each safety run-in cohort are presented in Table 1, Table 2, and Table 3, respectively. Dose de-escalation plans for each safety run-in cohort are presented in Table 4, Table 5, and Table 6, respectively. Schedules of treatment administration are provided in Appendix Table 6, Appendix Table 7, and Appendix Table 8.

Refer to Section 3.1.3 for information on Cohort 1 patients enrolled prior to implementation of Protocol Amendment 5.

Table 1. Dose Level and Schedule for Safety Run-in Cohort 1 (1L Unfit AML Mag+Ven+Aza)

	Dose Sched	Dose Schedule (Day per 28-Day Cycle)		
Drug/Dose/Route	Cycle 1	Cycle 2	Cycle 3+	
Azacitidine 75 mg/m ² SC or IV	Days 1-7 or Days 1-5, 8, 9 ^a	Days 1-7 or Days 1-5, 8, 9 ^a	Days 1-7 or Days 1-5, 8, 9 ^a	
Venetoclax PO	100 mg on Day 1 200 mg on Day 2 400 mg on Days 3-28	400 mg oi	n Days 1-28	
	Magrolimab Administration	n		
Magrolimab 1 mg/kg IV (over 3 hours)		Days 1, 4		
Magrolimab 15 mg/kg IV (over 3 hours)		Day 8		
Magrolimab 30 mg/kg IV (over 2 hours)	Days 11 and	Days 11 and 15, and then QW × 5 doses		
Magrolimab 30 mg/kg IV (over 2 hours)	Q2W beginning 1 we	Q2W beginning 1 week after the 5th weekly 30 mg/kg dose		

IV = intravenous; PO = orally; Q2W = every 2 weeks; QW = once weekly; SC = subcutaneous

Table 2. Dose Level and Schedule for Safety Run-in Cohort 2 (R/R AML Mag+MEC)

	Dose Schedule (D	Dose Schedule (Day per 28-Day Cycle)	
Drug/Dose/Route	Cycle 1	Cycle 2 to 3a	
Mitoxantrone 8 mg/m ² IV (over 15-30 min)	Days 1-5	Days 1-5	
Etoposide 100 mg/m ² IV (over 30-60 min)	Days 1-5	Days 1-5	
Cytarabine 1000 mg/m ² IV (over 1 hour)	Days 1-5	Days 1-5	
	Magrolimab Administration		
Magrolimab 1 mg/kg IV (over 3 hours)	Da	Days 1, 4	
Magrolimab 15 mg/kg IV (over 3 hours)	1	Day 8	
Magrolimab 30 mg/kg IV (over 2 hours)	Days 11 and 15, a	Days 11 and 15, and then QW × 5 doses	
Magrolimab 30 mg/kg IV (over 2 hours)		Q2W beginning 1 week after the 5th weekly 30 mg/kg dose, up to 12 months of total magrolimab treatment	

IV = intravenous; MEC = mitoxantrone, etoposide, cytarabine; Q2W= every 2 weeks; QW = once weekly

a Or any other alternative schedule, as long as 7 doses of azacitidine of the cycle are administered within 9 consecutive days.

a If patient achieved blast clearance after Cycle 1, one additional cycle of MEC will be given (total 2 cycles). If patient achieved blast clearance only after Cycle 2, a third cycle of MEC will be given. If no blast clearance at the end of Cycle 2, patient should be discontinued from the study.

Table 3. Dose Level and Schedule for Safety Run-in Cohort 3 (Post-Chemo Maint Mag+CC-486)

	Dose Sched	Dose Schedule (Day per 28-Day Cycle)		
Drug/Dose/Route	Cycle 1	Cycle 2	Cycle 3+	
CC-486 300 mg PO	Days 1-14	Days 1-14	Days 1-14	
	Magrolimab Administration			
Magrolimab 1 mg/kg IV (over 3 hours)		Days 1, 4		
Magrolimab 15 mg/kg IV (over 3 hours)		Day 8		
Magrolimab 30 mg/kg IV (over 2 hours)	Days 11 an	Days 11 and 15, and then QW × 5 doses		
Magrolimab 30 mg/kg IV (over 2 hours)	Q2W beginning 1 we	Q2W beginning 1 week after the 5th weekly 30 mg/kg dose		

IV = intravenous; PO = orally; Q2W= every 2 weeks; QW = once weekly

Table 4. Dose De-escalation for Safety Run-in Cohort 1 (1L Unfit AML Mag+Ven+Aza)

Dose Level	Dosing (28-Day Cycle)	
Venetoclax starting dose	Cycle 1: 100 mg PO Day 1, 200 mg Day 2, 400 mg Days 3-28, Cycle 2 and later: 400 mg Days 1-28	
Level Minus 1	Cycle 1: 100 mg PO Day 1, 200 mg Day 2, 400 mg Days 3-21, Cycle 2 and later: 400 mg Days 1-21	
Level Minus 2	Cycle 1: 100 mg PO Day 1, 200 mg Day 2, 400 mg Days 3-14, Cycle 2 and later: 400 mg Days 1-14	
Magrolimab and azacitidine (all dose levels)	Will be administered at the starting dose and not dose-reduced for any of the dose minus levels	

PO = orally

Table 5. Dose De-escalation for Safety Run-in Cohort 2 (R/R AML Mag+MEC)

	Dosing (28-Day Cycle)		
	MEC Magrolimab		
Dose Level	Cycles 1 and 2 to 3 ^a	Up to 12 Months	
Starting dose	Mitoxantrone 8 mg/m ² IV (over 15-30 min) Days 1-5 Etoposide 100 mg/m ² IV (over 30-60 min) Days 1-5 Cytarabine 1000 mg/m ² IV (over 1 hour) Days 1-5	Magrolimab: 1 mg/kg IV (over 3 hours) Days 1, 4; 15 mg/kg IV (over 3 hours) Day 8; 30 mg/kg IV (over 2 hours) Days 11 and 15, and then QW × 5 doses 30 mg/kg IV (over 2 hours) Q2W beginning 1 week after the 5th weekly 30 mg/kg dose	
Level Minus 1	Mitoxantrone 8 mg/m ² IV (over 15-30 min) Days 1-5 Etoposide 100 mg/m ² IV (over 30-60 min) Days 1-5 Cytarabine 1000 mg/m ² IV (over 1 hour) Days 1-5	Magrolimab: 1 mg/kg IV (over 3 hours) Days 1, 4; 15 mg/kg IV (over 3 hours) Day 8; 20 mg/kg IV (over 2 hours) Days 11 and 15, and then QW × 5 doses 20 mg/kg IV (over 2 hours) Q2W beginning 1 week after the 5th weekly 20 mg/kg dose	
Level Minus 2	Mitoxantrone 8 mg/m ² IV (over 15-30 min) Days 1-5 Etoposide 100 mg/m ² IV (over 30-60 min) Days 1-5 Cytarabine 1000 mg/m ² IV (over 1 hour) Days 1-5	Magrolimab: 1 mg/kg IV (over 3 hours) Days 1, 4; 15 mg/kg IV (over 3 hours) Day 8; 15 mg/kg IV (over 2 hours) Days 11 and 15, and then QW × 5 doses 15 mg/kg IV (over 2 hours) Q2W beginning 1 week after the 5th weekly 15 mg/kg dose	

IV = intravenous; MEC = mitoxantrone, etoposide, cytarabine; QW = once weekly; Q2W= every 2 weeks

a If patient achieved blast clearance after Cycle 1, one additional cycle of MEC will be given (total 2 cycles). If patient achieved blast clearance only after Cycle 2, a third cycle of MEC will be given. If no blast clearance at the end of Cycle 2, patient should be discontinued from the study.

Table 6. Dose De-escalation for Safety Run-in Cohort 3 (Post-Chemo Maint Mag+CC-486)

Dose Level	Dosing (28-Day Cycle) (Cycles 1, 2, and 3+)	
CC-486 Starting dose	300 mg PO Days 1-14	
Level Minus 1	200 mg PO Days 1-14	
Level Minus 2	200 mg PO Days 1-7	
Magrolimab (all dose levels)	Magrolimab will be administered at the starting dose and will not be dose-reduced for any of the dose minus levels	

PO = per oral route

3.3. Duration of Treatment

Cohorts 1 and 3: treatment until discontinuation criteria is met.

Cohort 2: treatment for up to 12 months.

Patients in each safety run-in cohort will receive 1 cycle (28 days) of study treatment before being evaluated for DLTs. Patients in the safety run-in cohorts will continue study treatment at the assigned dose level for at least 4 cycles, after which they may continue at the assigned dose level or switch to the RP2D upon agreement between the investigator and the sponsor. Safety run-in cohort patients will continue dosing until Phase 2 cohort end-of-treatment criteria are met.

Patients in Phase 2 Cohorts 1 and 3 will receive study treatment until disease progression, unacceptable toxicity, and/or loss of clinical benefit.

Patients in Phase 2 Cohort 2 will receive MEC for 2 to 3 cycles. Patients who do not achieve an OR (ie, CR, CRi, CRh, PR, or MLFS) after 2 cycles will be discontinued from therapy. For patients achieving a response after 1 to 2 cycles, an additional single MEC cycle will be administered. Magrolimab will be administered in Phase 2 Cohort 2 until disease progression, unacceptable toxicity, and/or loss of clinical benefit for up to 12 months.

3.4. Discontinuation Criteria

Reasons for discontinuation of study treatment must include, but are not limited to, the following:

- Disease progression (including treatment failure and relapse)
- Unacceptable toxicity
- Loss of clinical benefit
- Death
- Pregnancy during the study

- Patient request, with or without a stated reason
- Patient noncompliance
- Initiation of anti-AML therapy
- SCT
- Investigator or treating physician decision
- Protocol violation
- Lost to follow-up
- Discontinuation of the study at the request of Gilead, a regulatory agency, or an institutional review board (IRB)/independent ethics committee (IEC)

Although disease progression is considered a sufficient reason for discontinuing a patient from study treatment, given the delayed treatment benefit commonly seen in immune therapies, the investigator is advised to continue to treat the patient until the investigator considers the study treatment to be no longer clinically beneficial to the patient, or the change of disease state renders the patient unacceptable for further treatment in the judgment of the investigator. All patients must be followed through completion of all study treatments.

If patients remain on study drugs beyond disease progression, a second bone marrow assessment, along with required laboratory tests for response assessment, should be done within 4 weeks. If disease progression is confirmed at the second bone marrow assessment, the patient should be discontinued from the study treatment.

Patients who discontinue study treatment are to return for an end-of-treatment (EOT) visit for evaluation of safety within 7 days (\pm 7 days) of their last dose or the decision to end study treatment, whichever is later. In addition, patients are to have a safety follow-up telephone call 30 days and 70 days (\pm 7 days) after their last dose of study treatment. When a serious adverse event (SAE) or treatment-related AE is reported during the telephone call, the patient should come to the clinic for physical examination and blood tests, if clinically needed. Follow-up for ongoing SAEs or treatment-related AEs after the safety follow-up visit/call will stop if a patient begins another anti-AML therapy.

When considering SCT, note that no significant magrolimab-related transplant complications have been observed in patients who have achieved a response and undergone SCT in an ongoing magrolimab study in AML and MDS (Study 5F9005); however, a 4-week wash-out period for magrolimab is recommended prior to SCT.

If a patient discontinues study dosing (for example, as a result of an AE), every attempt should be made to keep the patient in the study and continue to perform the required study-related follow-up and procedures. If this is not possible or acceptable to the patient or investigator, the patient may be withdrawn from the study.

The assessments to be performed at each of the posttreatment visits are listed in Appendix Table 9.

Refer to Section 3.1.3 for information on Cohort 1 patients enrolled prior to implementation of Protocol Amendment 5.

3.5. End of Study

All Patients: The end of the entire study for all patients is defined as the date on which the last patient remaining on study completes the last study visit/call or when the sponsor decides to end the study. The sponsor reserves the right to terminate the study at any time for any reason (including safety).

Individual Patients: Patients are considered to have completed study participation altogether when they are no longer followed for safety.

3.6. Poststudy Care

Upon withdrawal from study treatment, patients will receive the care upon which they and their physicians agree. Patients will be followed for AEs as specified in Appendix Table 9.

3.7. Source Data

The source data for this study will be obtained from original records (eg, clinic notes, hospital records, patient charts), local and/or specialty (PK, ADA, and/or PD) laboratory testing, and/or additional biomarker testing.

3.8. Pharmacokinetics/Biomarker Testing

[figure not shown]
3.8.1. Biomarker and Genomic Samples to Address the Study Objectives

Peripheral blood, bone marrow aspirate and trephine biopsy, and buccal swab samples will be collected from all patients who have provided consent to participate in this study at the time points listed in the schedules of assessments (Appendix Table 1, Appendix Table 2, Appendix Table 3, Appendix Table 4, Appendix Table 5, and Appendix Table 9). The samples may be used to evaluate the association of systemic and/or tissue-based biomarkers with study treatment response, including efficacy and/or AEs, and dosage selection, and to better understand the biological pathways involved in AML pathogenesis and the immune response to AML, as well as the efficacy and MOA for magrolimab combinations. Because biomarker science is a rapidly evolving area of investigation, and AEs in particular are difficult to predict, it may not be possible to specify prospectively all tests that may be done on the specimens provided. The specific analyses will include, but may not be limited to, the biomarkers and assays described below. The testing outlined below is based upon the current state of scientific knowledge. It may be modified during or after the end of the study to remove tests no longer indicated and/or to add new tests based upon new state of the art knowledge.

The blood, bone marrow, and buccal swab samples collected will be used to measure biomarkers, which may include but will not be limited to the frequency of leukemia stem cells or MRD, presence of or changes to immune cell populations, secreted protein factors, the expression of cell surface markers on either tumor cells or cells of the tumor microenvironment, and genetic mutations in tumor cells or subclones of tumor cells.

The samples will also be used for genomic research to identify or validate genetic markers that may increase our knowledge and understanding of the biology of the study disease and related diseases, and to study the association of genetic markers with disease pathogenesis, progression, and/or treatment outcomes, including efficacy, AEs, and the processes of drug absorption and disposition. These specimens may also be used to develop biomarker or diagnostic assays and establish the performance characteristics of these assays. Genomics research may include sequencing of genetic material derived from both cancer cells and normal cells. Sequencing of genetic material derived from cancer cells will be used to better understand the MOA of magrolimab combinations in this patient population, and potentially to identify subsets of patients who are likely to benefit. Sequencing of genetic material derived from normal cells will be used to define differences in sequences that are cancer specific.

Samples collected for biomarker assessments will be destroyed no later than 15 years after the end of study or in accordance with country requirements.

4. PATIENT POPULATION

4.1. Number of Patients and Patient Selection

Up to approximately 164 patients will be enrolled in the study, with up to 54 patients in the safety run-in cohorts and up to 110 patients in the Phase 2 cohorts.

Refer to Section 3.1.3 for information on Cohort 1 patients enrolled prior to implementation of Protocol Amendment 5.

The following patient populations will be enrolled into the study:

- Safety Run-in Cohort 1 and Phase 2 Cohort 1 (1L Unfit AML Mag+Ven+Aza), closed to enrollment globally as of Protocol Amendment 5: patients with newly diagnosed, previously untreated AML confirmed based on World Health Organization (WHO) criteria who are age 75 years or older, or who are age 18 years to 74 years and have comorbidities that preclude the use of intensive chemotherapy
- Safety Run-in Cohort 2 and Phase 2 Cohort 2 (R/R AML Mag+MEC): patients with confirmation of AML by WHO criteria who are refractory to or have relapsed after the initial intensive chemotherapy
- Safety Run-in Cohort 3 and Phase 2 Cohort 3 (Post-chemo Maint Mag+CC-486), closed to enrollment globally as of Protocol Amendment 5: patients with confirmation of AML by WHO criteria who achieved CR or CRi with presence of MRD (MRD positive) after intensive induction chemotherapy with or without consolidation therapy prior to starting maintenance therapy

4.1.1. Patient Replacement

For the safety run-in cohorts, patients who do not meet the DLT assessment criteria will be replaced. In the Phase 2 cohorts, there will be no patient replacement.

4.2. Inclusion Criteria

All Patients

All patients must meet the following inclusion criteria to be eligible for participation in this study:

1) White blood cell (WBC) count $\leq 20 \times 10^3/\mu L$ prior to first dose of study treatment. If the patient's WBC count is $\geq 20 \times 10^3/\mu L$ prior to first dose of study treatment, the patient can be enrolled, assuming all other eligibility criteria are met. However, ensure that the WBC count is $\leq 20 \times 10^3/\mu L$ prior to the first dose of study treatment and prior to each magnolimab dose for the first 4 weeks.

NOTE: Patients can be treated with hydroxyurea and/or leukapheresis throughout the study or prior to first dose of study treatment to reduce the WBC count to $\leq 20 \times 10^3/\mu L$ to enable eligibility for magrolimab dosing.

2) Hb must be ≥ 9 g/dL prior to initial dose of study treatment

NOTE: Transfusions are allowed to meet Hb eligibility (see Section 7.8.1.1).

- 3) Adequate liver function as demonstrated by the following:
 - a) AST $\leq 3.0 \times$ upper limit of normal (ULN)
 - b) ALT $\leq 3.0 \times ULN$
 - c) bilirubin $\leq 1.5 \times \text{ULN}$, or $\leq 3.0 \times \text{ULN}$ and primarily unconjugated if patient has a documented history of Gilbert syndrome or genetic equivalent.
- 4) Patients must have adequate renal function as demonstrated by a creatinine clearance (CLcr) ≥ 30 mL/min calculated by the Cockcroft-Gault formula.
- 5) Patient has provided informed consent.
- 6) Patient is willing and able to comply with clinic visits and procedures outlined in the study protocol.
- 7) Male or female, age \geq 18 years.
- 8) Pretreatment blood cross-match completed (as detailed in Section 6.5.3).
- 9) Male patients and female patients of childbearing potential who engage in heterosexual intercourse must agree to use protocol-specified method(s) of contraception as described in Appendix 5.
- 10) Patients must be willing to consent to mandatory pretreatment and on-treatment bone marrow biopsies (trephines), unless not feasible as determined by the investigator and discussed with the sponsor.

Safety Run-in Cohort 1 and Phase 2 Cohort 1 (1L Unfit AML Mag+Ven+Aza), closed to enrollment globally as of Protocol Amendment 5

In addition to meeting the inclusion criteria for all patients, patients who are enrolled into Safety Run-in Cohort 1 and Phase 2 Cohort 1 must fulfill the following cohort-specific inclusion criteria:

CONFIDENTIAL Page 61 02 November 2023

- 11) Newly diagnosed, previously untreated patients with confirmation of AML by WHO criteria who are ineligible for treatment with a standard cytarabine and anthracycline induction regimen due to age, comorbidity, or other factors. Patients must be considered ineligible for induction therapy defined by the following:
 - a) ≥ 75 years of age
 - b) \geq 18 to 74 years of age with at least 1 of the following comorbidities:
 - i. ECOG performance status of 2 or 3
 - ii. Diffusing capacity of the lung of carbon monoxide $\leq 65\%$ or forced expiratory volume in 1 second $\leq 65\%$
 - iii. LVEF $\leq 50\%$
 - iv. CLcr < 45 mL/min calculated by the Cockcroft-Gault formula
 - v. Any other comorbidity that the investigator judges to be incompatible with intensive chemotherapy that must be approved by the sponsor medical monitor before study enrollment.
- 12) ECOG performance status:
 - Of 0 to 2 for subjects \geq 75 years of age

OR

- Of 0 to 3 for subjects \geq 18 to 74 years of age
- 13) Patients who have not received prior anti-leukemia therapy for AML (excluding hydroxyurea), HMA, low-dose cytarabine, and/or venetoclax.
 - NOTE: Patients with prior MDS who have not received prior HMA, venetoclax, or a chemotherapeutic agent are eligible. Other prior MDS therapies, including but not limited to lenalidomide, erythroid stimulating agents, or similar RBC-, WBC-, or platelet direct therapies or growth factors, are allowed.
- 14) Patients who have not received strong and/or moderate cytochrome P450 enzyme (CYP) 3A inducers (eg, St. John's Wort) within 7 days prior to the initiation of study treatment.
- 15) Patients who have not consumed grapefruit, grapefruit products, Seville oranges (including marmalade containing Seville oranges) or starfruit within 3 days prior to the initiation of study treatment or are willing to discontinue consumption of these while receiving study drug.

CONFIDENTIAL Page 62 02 November 2023

16) Patients without malabsorption syndrome or other conditions that preclude enteral route of administration.

Safety Run-in Cohort 2 and Phase 2 Cohort 2 (R/R AML Mag+MEC)

In addition to meeting the inclusion criteria for all patients, patients who are enrolled into Safety Run-in Cohort 2 and Phase 2 Cohort 2 must fulfill the following cohort-specific inclusion criteria:

17) Patients with confirmation of AML by WHO criteria who are refractory to or have experienced first relapse after initial intensive chemotherapy, which includes 1 or 2 cycles of a 7 + 3 based induction regimen or a purine analogue based induction therapy, such as fludarabine or cladribine paired with anthracyclines and cytarabine (eg, fludarabine, high-dose cytarabine [ara-C], G-CSF, and idarubicin [FLAG-Ida] or cladribine, ara-C, G-CSF, and mitoxantrone [CLAG-M]) or failed therapy after remission (eg, consolidation) during any number of cycles (maximum of 4) of high- or intermediate-dose cytarabine. For other intensive regimens, please discuss with the medical monitor.

NOTE: Patients who are relapsed after or are refractory to more than 1 line of anti-AML treatment are not eligible.

Patients who relapsed after undergoing stem cell transplant may be eligible.

18) At least 2 weeks must have elapsed since any prior anti-leukemia agents.

NOTE: Localized non-central nervous system (CNS) radiotherapy, hydroxyurea, and erythroid and/or myeloid growth factors are not criteria for exclusion.

- 19) ECOG performance status of 0 to 2.
- 20) Patients with LVEF ≥ 50%, lack of symptomatic congestive heart failure, or clinically significant cardiac arrhythmias.
- 21) Patients who have not been treated with trastuzumab within 7 months prior to the initiation of study treatment
- 22) Patients who have not previously received maximum cumulative doses of anthracyclines and anthracenediones
- 23) Patients without degenerative or toxic encephalopathies
- 24) Patients who did not undergo hematopoietic SCT in the past 100 days, are not on immunosuppressive therapy post SCT in the 2 weeks prior to the first dose of study treatment, or have no active clinically significant graft-versus-host disease.

Safety Run-in Cohort 3 and Phase 2 Cohort 3 (Post-chemo Maint Mag+CC-486), closed to enrollment globally as of Protocol Amendment 5

In addition to meeting the inclusion criteria for all patients, patients who are enrolled into Safety Run-in Cohort 3 and Phase 2 Cohort 3 must fulfill the following cohort-specific inclusion criteria:

- 25) Patients with confirmation of AML by WHO criteria who achieved a CR or CRi with presence of MRD (MRD positive by local flow cytometry assay, defined as ≥ 0.1% detectable MRD) after intensive induction chemotherapy with or without consolidation therapy, prior to starting maintenance therapy for newly diagnosed AML.
- 26) ECOG performance status of 0 to 2.
- 27) Patients without malabsorption syndrome or other conditions that preclude enteral route of administration.

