- 21) Patients who have not been treated with trastuzumab within 7 months prior to the initiation of study treatment
- 22) Patients who have not previously received maximum cumulative doses of anthracyclines and anthracenediones
- 23) Patients without degenerative or toxic encephalopathies
- 24) Patients who did not undergo hematopoietic stem cell transplantation (SCT) in the past 100 days, are not on immunosuppressive therapy post SCT in the 2 weeks prior to the first dose of study treatment, or have no active clinically significant graft-versus-host disease.

Safety Run-in Cohort 3 and Phase 2 Cohort 3 (Post-chemo Maint Mag+CC-486), closed to enrollment globally as of Protocol Amendment 5

- 25) Patients with confirmation of AML by WHO criteria who achieved a CR or CRi with presence of MRD (MRD positive by local flow cytometry assay, defined as ≥ 0.1% detectable MRD) after intensive induction chemotherapy with or without consolidation therapy, prior to starting maintenance therapy for newly diagnosed AML.
- 26) ECOG performance status of 0 to 2.
- 27) Patients without malabsorption syndrome or other conditions that preclude enteral route of administration.

Exclusion Criteria

All Patients

- 1) Positive serum pregnancy test.
- 2) Breastfeeding female.
- 3) Known hypersensitivity to any of the study drugs, the metabolites, or formulation excipient
- 4) Patients who received any live vaccine within 4 weeks prior to initiation of study treatments.
- 5) Prior treatment with cluster of differentiation 47 (CD47) or signal regulatory protein alpha (SIRPα)-targeting agents.
- 6) Current participation in another interventional clinical trial.
- 7) Known inherited or acquired bleeding disorders.
- 8) Clinical suspicion of or documented active CNS involvement with AML.
- 9) Patients who have acute promyelocytic leukemia.
- 10) Significant disease or medical conditions, as assessed by the investigator and sponsor, that would substantially increase the risk:benefit ratio of participating in the study. This includes, but is not limited to, acute myocardial infarction within the last 6 months, unstable angina, uncontrolled diabetes mellitus, significant active infections, and congestive heart failure New York Heart Association Class III-IV.

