4.3. Exclusion Criteria

Patients who meet *any* of the following exclusion criteria are not to be enrolled in this study:

- 1) Positive serum pregnancy test (Appendix 5).
- 2) Breastfeeding female.
- 3) Known hypersensitivity to any of the study drugs, the metabolites, or formulation excipient.
- 4) Patients who received any live virus vaccine within 4 weeks prior to initiation of study treatments.
- 5) Prior treatment with CD47 or SIRPα-targeting agents.
- 6) Current participation in another interventional clinical trial.
- 7) Known inherited or acquired bleeding disorders.
- 8) Clinical suspicion of or documented active CNS involvement with AML.
- 9) Patients who have acute promyelocytic leukemia.
- 10) Significant disease or medical conditions, as assessed by the investigator and sponsor, that would substantially increase the risk:benefit ratio of participating in the study. This includes, but is not limited to, acute myocardial infarction within the last 6 months, unstable angina, uncontrolled diabetes mellitus, significant active infections, and congestive heart failure New York Heart Association Class III-IV.

- 11) Second malignancy, except MDS, treated basal cell or localized squamous skin carcinomas, localized prostate cancer, or other malignancies for which patients are not on active anticancer therapies and have had no evidence of active malignancy for over 1 year. Previous hormonal therapy with luteinizing hormone-releasing hormone (LHRH) agonists for prostate cancer and treatment with bisphosphonates and receptor activator of nuclear factor kappa-B ligand (RANKL) inhibitors are not criteria for exclusion.
 - NOTE: Patients on maintenance therapy alone who have no evidence of active malignancy for at least ≥ 1 year are eligible.
- 12) Known medical history of active or chronic hepatitis B or C infection or medical history of human immunodeficiency virus (HIV) infection.

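### Cohort 2 inclusion criterion 24 joins its three post-transplant conditions with 'or', so read literally any one of them is enough

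*Protocol*

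**What the plan says.** Section 4.2 opens the Cohort 2 list by saying that these patients have to meet the cohort-specific criteria as well as those for all patients. Criterion 24 begins "Patients who did not undergo hematopoietic SCT in the past 100 days, are not on immunosuppressive therapy post SCT in the 2 weeks" and ends "prior to the first dose of study treatment, or have no active clinically significant graft-versus-host disease". The synopsis carries the same criterion with the same connective: "or have no active clinically significant graft-versus-host disease".

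Criterion 17, in the same list, says "Patients who relapsed after undergoing stem cell transplant may be eligible". Patients with a transplant history are therefore expected candidates for this cohort.

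Section 4.3 contains no exclusion that names transplant, GVHD or immunosuppression. Its nearest clause is exclusion 10: "Significant disease or medical conditions, as assessed by the investigator and sponsor, that would substantially increase the risk:benefit ratio". This is a judgement made by the investigator and the sponsor. Its list of examples is expressly open-ended and mentions none of the three conditions.

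Criterion 20, also for Cohort 2, requires an LVEF of at least 50% and continues "lack of symptomatic congestive heart failure, or clinically significant cardiac arrhythmias". The synopsis has the same wording.

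**The concern.** Criterion 24 is a condition to be fulfilled, not a bar. In a list of bars, *or* is the right connective, because any one item keeps the patient out. In a list of requirements, *or* has the opposite effect, because any one item lets the patient through. Each limb of criterion 24 is already phrased as a negated requirement, so the connective works against the purpose of the criterion.

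This is the one numbered criterion that addresses how recent the transplant was, whether immunosuppression is continuing and whether GVHD is active. If its wording does not require all three, sites can reach different answers on the same patient. A site that enrolls on the literal text could not clearly be said to have deviated. Cohort 2 is the cohort that Amendment 5 did not close (Section 3.1.3). A patient admitted this way and dosed enters the Full Analysis Set (Section 8.3.1.1), and Phase 2 patients are not replaced (Section 4.1.1).

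**Working it through.** No arithmetic in the plan bears on this point. The check is a reading of the text.

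**Limbs of criterion 24 (Section 4.2; same in the synopsis)**
- A: no transplant in the last 100 days.
- B: not on post-transplant immunosuppression in the two weeks before the first dose.
- C: no active clinically significant GVHD.

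As written, the criterion is A *or* B *or* C. The evident intent is A *and* B *and* C.

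**Three constructed patients, each relapsed after transplant**

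| Patient | A | B | C | As written | If all apply |
|---|---|---|---|---|---|
| Six months after transplant, on immunosuppression, active GVHD | met | not met | not met | meets criterion 24, through A | does not meet |
| 40 days after transplant, on immunosuppression, no GVHD | not met | not met | met | meets criterion 24, through C | does not meet |
| 40 days after transplant, off immunosuppression, active GVHD | not met | met | not met | meets criterion 24, through B | does not meet |

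On the literal text, only a patient who fails all three limbs at once is stopped by this criterion. A patient who has never had a transplant meets it on either reading.

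**Can the *or* be read as *and* from the grammar?** Criteria 16 and 23 place a single negation in front of a list joined by *or*, so the negation covers every item and *or* is correct there. In criterion 24 each limb has its own verb and its own negation, so no single negation spans the list. Criterion 15 has the same construction (patients who have not done one thing, or are willing to do another), and there *or* marks a true alternative. A site that reads criterion 24 as it reads criterion 15 is being consistent.

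**Is the gap closed elsewhere?** Not by any named exclusion in Section 4.3. The Cohort 2 prohibited-medication section (5.3.7) does not name immunosuppressants either, though it also refers sites to local prescribing information. Exclusion 10 can be used, but only by judgement.

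**Criterion 20.** Two readings are open. If the words for absence govern both heart failure and arrhythmia, the LVEF limb stands beside them as its own requirement, although no *and* says so. If the three items are read as a flat list, one limb would suffice and the third would lose its negation. The first reading is the more natural.

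**The case against.** The strongest reply is that no sensible site would read criterion 24 as three alternatives. On that reading, every patient more than 100 days from transplant passes on limb A, and the immunosuppression and GVHD limbs do almost nothing. The intent is plain, and nothing in the protocol shows that any site read it otherwise. This stands as to intent. It does not change the text, which is the same in two places and is what a site or monitor has to apply.

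Exclusion 10 is also a real backstop. Its examples are not exhaustive, and active GVHD could be barred under it. This stands too, so a reader who infers that nothing else in the protocol could keep such a patient out goes too far. So does one who infers that the patient qualifies for the study: the patient meets criterion 24 only, must still meet every other criterion, and under criterion 17 only *may* be eligible.

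Three further readings are tempting and are not supported:
- **That criterion 20 has the same error.** Its wording for absence naturally covers both heart failure and arrhythmia. Section 6.2.1 also requires an echocardiogram or MUGA for Cohort 2 if none was done in the 30 days before consent, and Section 7.8.4 calls for LVEF evaluation before mitoxantrone. It is ambiguous, not wrong.
- **That the effect can be measured by counting combinations of the three conditions, or as a share of the sample size or of the toxicity trigger.** Such counts treat logical cells as if they were patients, or assume an outcome for a patient who may never be enrolled.
- **That admitted patients would shift the complete remission rate or the dose-limiting toxicity count through poorer blood count recovery.** The protocol states no such link for GVHD or immunosuppression.

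**Conclusion.** Criterion 24 is wrong as written, in Section 4.2 and in the synopsis. It lets a Cohort 2 patient meet a three-part safety screen on one part, while the evident intent is that all three apply. The only remaining protection for these conditions in the exclusion list is the discretionary clause in exclusion 10.

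The conclusion rests on the ordinary meaning of the connective in an inclusion list, and on criterion 17 leaving the cohort open to patients who relapsed after transplant. The number of patients affected cannot be derived: the protocol gives no expected frequency of prior transplant, immunosuppression or GVHD, and no evidence that anyone has been wrongly enrolled. Criterion 20 is a secondary point of clarity.

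**What to change.** In Section 4.2 and in the synopsis, restate criterion 24 as three separate requirements joined by *and*, using the conditions already there: the 100-day transplant interval, the two-week immunosuppression interval, and the absence of active clinically significant GVHD. No threshold changes.

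In the same edit, reword criterion 20 in both places so that the existing LVEF, heart failure and arrhythmia conditions are unmistakably separate requirements.

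The cost is a few words in two places at the next amendment. No patient whom the criteria were meant to admit is lost, and no analysis changes.
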